5.19. Definition of Study Interruption

Study interruption will be defined as any interruption lasting ≥ 2 weeks and allowed up to 4 weeks (+4 days). that is due to any causes related COVID-19 pandemic and will require extra handling when deriving analysis visits.

[figure not shown]
5.20. Definition of Actual Time

For PK analysis, actual time will be defined as:

Actual Time=Actual Sample Collection Time - Actual Last Dosing Time (before the corresponding sample collection)

6. Potential Covariates

The stratification factor of biopsy confirmed NASH with fibrosis status (F1, F2, F3) Yes or No will be considered as a potential covariate to be adjusted for in the statistical models.

Subgroup analyses will be descriptive in nature.

8. Analysis Populations

The number of subjects in each analysis population by treatment group will be summarized.

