3.3. Randomization Schedule and Blinding Procedures

Eligible subjects will be randomized in the order they are enrolled into the study. For Cohort 1, eight eligible subjects will be randomized in a 3:1 ratio to active (BIO89-100): control (placebo). For Cohort 2, fifteen subjects will be randomized in a 4:1 ratio to active: control. For cohorts 4 and 6, twelve eligible subjects will be randomized in each cohort in a 3:1 ratio to active: control. For Cohorts 3 and 5, eighteen subjects will be randomized in each cohort in a ratio of 7:2 active: control, stratified by biopsy confirmed NASH with fibrosis status F1, F2 or F3 (Yes, No), with each stratum of nine subjects in each cohort.

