3.4. Stratification Factors

Cohorts 3 and 5, will be stratified by biopsy confirmed NASH with fibrosis status F1, F2 or F3 (Yes, No).

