3.5. Sample Size and Power

No formal sample size calculation was performed for the primary endpoint(s) as the total of approximately 83 subjects, consisting of 6:2 (Cohort 1), 12:3 (Cohort 2), 9:3 (Cohorts 4 and 6) or 14:4 (Cohorts 3 and 5) receiving active: placebo, respectively is considered adequate to inform on the endpoints for this Phase 1b study.

A power assessment based on magnetic resonance imaging – proton density fat fraction (MRI-PDFF) endpoint (percent change from baseline to End of Treatment in liver fat content, an important biomarker) shows that 9, 12 and 14 subjects in a dose cohort compared to the pooled 19 placebo subjects will provide [REDACTED] power, respectively, to detect a difference in mean percentage change from baseline between treatment groups of [REDACTED], assuming

a standard deviation of █ in each group. Calculation was based on two-sample one-sided t-test with alpha at 0.05 (e.g., two-sided alpha at 0.10).

Subjects who withdraw from the study before the Day 50 assessments may be replaced at the discretion of the Sponsor.

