9.1.2. Statistical Modeling Methods

A mixed model repeated measures (MMRM) analysis will be used to analyze the change from baseline and/or percent change from baseline in the pharmacodynamic endpoints. The model will include baseline as a covariate, treatment group, visit, and the interaction between treatment group and visit as factors. The covariance will be unstructured; if the model fails to converge, other structures such as compound symmetry will be considered. The LS means and the LS mean difference will be presented by visit with their corresponding standard error, p-values and two-sided 90% and 95% confidence intervals.

If strong evidence exists that the normality assumptions are violated for, but not limited to, triglycerides or MRI-PDFF, non-parametric methods will be considered such as the Wilcoxon Rank Sum test.

There will be no adjustments for multiplicity in this study.

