13.1. Sample SAS Code

Sample SAS Code for MMRM analysis:

```
proc mixed data=indata;
class trt visit;
model chg /*or pchg*/ = base trt visit trt*visit/ ddfm=kr s;
repeated visit/type=UN subject=usubjid;
lsmeans trt*visit/pdiff cl alpha=0.1;
run;
```

Sample SAS Code for MMRM analysis with Fibrosis Status Y/N as factor:

```
proc mixed data=indata;
class trt visit biopsy_confirmed_NASH_yn;
model chg /*or pchg*/ = base trt visit biopsy_confirmed_NASH_yn trt*visit/
ddfm=kr s;
repeated visit/type=UN subject=usubjid;
lsmeans trt*visit/pdiff cl alpha=0.1;
run;
```

Sample SAS Code for Wilcoxon Rank Sum Non-Parametric analysis:

```
proc npar1way data=indata wilcoxon alpha=0.1;
class trt;
var chg /*or pchg*/;
exact wilcoxon;
run;
```

Sample SAS Code for Hedges-Lehman Estimation:

```
proc npar1way data=indata hl alpha=0.1;
class trt;
var chg /*or pchg*/;
exact hl;
run;
```

Sample SAS Code for Multiple Imputation Using Control Based Pattern-Mixture Model:

```
proc mi data = non_mono out=monotone niimpute=100 seed=123;
var trt01pn day50 day92;
mcmc chain = multiple impute=monotone;
run;
```

Note: Data needs to be in wide format for the multiple imputation procedure Also, dummy variables are need for categorical factors with more than two levels such as TREATMENT.

```
proc mi data=monotone out=imputed1 nimpute=1 seed = 124;
by _imputation_;
class trt01pn;
var trt01pn day50 day92;
monotone reg(/details);
mnar model (day50 day92/modelobs=( trt01pn ='0')) ;
run;
```

```
proc mixed data=imputed;
by _imputation_;
class subject trt visit;
model pchg = base trt visit trt *visit/ddfm=kr;
repeated visit / sub=subject type=un;
lsmeans trt *visit/pdiff cl;
ods output lsmeans=lsmeans diffs=diffs;
run;
proc sort data=lsmeans;
by trt visit _imputation;
run;
proc mianalyze parms=lsmeans;
modeleffects trt * visit;
ods output parameterestimates=lsm;
by trt visit;
run;
proc sort data=diffs;
by visit _imputation;
run;
proc mianalyze parms=diffs;
modeleffects trt * visit;
ods output parameterestimates=dif;
by visit;
run;
```

BIO89-100-002 (Part 2)
NCT #: NCT04048135

Page 1 of 41

Statistical Analysis Plan

[figure not shown]
Protocol BIO89-100-002 (Part 2, Single Cohort)

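### The Part 1 MMRM omits the randomisation stratum, and the pooled placebo group is not protected against imbalance on it

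*SAP*

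**What the plan says.** All references are to the Part 1 SAP unless stated.

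- **Model.** Section 9.1.2 states: "The model will include baseline as a covariate, treatment group, visit, and the interaction between treatment group and visit as factors". The first code block in Appendix 13.1 matches it: "model chg /*or pchg*/ = base trt visit trt*visit/ ddfm=kr s".
- **Stratum as covariate.** Section 6 says that the stratification factor "will be considered as a potential covariate to be adjusted for in the statistical models". It gives no rule for when, or for which endpoints, the factor enters.
- **Second model.** Appendix 13.1 has another block, titled "Sample SAS Code for MMRM analysis with Fibrosis Status Y/N as factor", which adds `biopsy_confirmed_NASH_yn` as a main effect. No visible section refers to it.
- **Design.** Only Cohorts 3 and 5 are stratified (3.4). Section 3.3 says that "eighteen subjects will be randomized in each cohort in a ratio of 7:2 active: control", "with each stratum of nine subjects in each cohort".
- **Control group.** Placebo subjects from all cohorts form one group (5.10, 9.1), and the power assessment in 3.5 compares each dose with all 19 of them.
- **MRI-PDFF.** The supportive analyses in 9.4.3.2 are multiple imputation, correlation and a rank-based analysis. A stratum-adjusted MMRM is not among them.

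**The concern.** A factor used to restrict randomisation normally belongs in the analysis model. Here there is a further reason. Randomisation balances the factor between active and placebo within a cohort, but the analysis compares each dose with placebo subjects drawn from every cohort. Within-cohort randomisation does not protect those contrasts. If biopsy-confirmed NASH with fibrosis predicts change in MRI-PDFF, ALT or Pro-C3 beyond the baseline value, part of a dose-versus-placebo difference could reflect case mix.

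The stratified and unstratified dose groups would also be shifted in opposite directions. That bears on comparisons between doses, and protocol 3.2.1 says the Part 1 data are meant to inform dose selection. Finally, a plan that holds an unadjusted and an adjusted model, with no stated role for the second, leaves its use to be settled after results are known.

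**Working it through.** **Inputs.** Active:placebo by cohort, 1 to 6: 6:2, 12:3, 14:4, 9:3, 14:4, 9:3 (SAP 3.5 and Table 1). Stratum size 9 and ratio 7:2 in Cohorts 3 and 5 (3.3). The Yes share p in Cohorts 1, 2, 4 and 6 is not given. In protocol 3.3.1 biopsy is optional, and there are two entry routes without one, so p is varied from 0 to 100% and taken as common to those cohorts.

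**The plan's own figures.** Placebo: 2 + 3 + 4 + 3 + 4 + 3 = 19. Active: 6 + 12 + 14 + 9 + 14 + 9 = 64. Total: 83. Both 19 and 83 are reproduced. The power figure cannot be, because the difference, SD and power are blacked out.

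**Composition.** Nine subjects at 7:2 give 7 active and 2 placebo per stratum. Each 18 mg group is 7 Yes and 7 No. The two cohorts together give 4 Yes and 4 No placebo. The other 19 − 8 = 11 placebo subjects have an expected Yes share p.

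- Pooled placebo Yes share = (4 + 11p)/19
- Cohort 3 or 5 active minus placebo = 0.5 − (4 + 11p)/19 = 11(0.5 − p)/19
- Cohort 1, 2, 4 or 6 active minus placebo = p − (4 + 11p)/19 = 8(p − 0.5)/19
- Cohort 3 or 5 active minus other active = 0.5 − p

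| p | Placebo Yes | 3/5 minus placebo | Others minus placebo | 3/5 minus others |
|---|---|---|---|---|
| 0% | 21.1% | +28.9 | −21.1 | +50 |
| 10% | 26.8% | +23.2 | −16.8 | +40 |
| 25% | 35.5% | +14.5 | −10.5 | +25 |
| 50% | 50.0% | 0 | 0 | 0 |
| 75% | 64.5% | −14.5 | +10.5 | −25 |
| 100% | 78.9% | −28.9 | +21.1 | −50 |

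Differences are in percentage points.

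**Bias.** Expected bias = stratum effect × imbalance. With an assumed effect of 0.5 SD, the largest values are 0.5 × 0.289 = 0.145 SD (Cohorts 3 and 5 against placebo), 0.5 × 0.211 = 0.105 SD (the others against placebo) and 0.5 × 0.50 = 0.25 SD (between the two sets of doses). At p = 10% they are 0.116, 0.084 and 0.20 SD.

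**Effect of adjusting.** A simulation used 83 subjects, seven groups, one visit, no treatment effect, within-stratum SD 1 and 3,000 runs per setting:

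| p | Stratum effect | Cohort | Bias without → with stratum (SD) | SE without → with stratum |
|---|---|---|---|---|
| 10% | 0.5 SD | 3 | 0.115 → −0.001 | 0.359 → 0.357 |
| 10% | 0.5 SD | 4 | −0.093 → −0.007 | 0.413 → 0.407 |
| 10% | 1.0 SD | 3 | 0.223 → −0.007 | 0.381 → 0.357 |
| 10% | 1.0 SD | 4 | −0.177 → −0.004 | 0.438 → 0.407 |

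Runs at p = 25% gave the same pattern. Over all eight cohort-and-setting results, the adjusted bias stayed within 0.013 SD and the adjusted SE was never larger. The unadjusted two-sided 10% test rejected 13.7% of the time in the worst case (Cohort 3, p = 10%, 1.0 SD), against 9.4% adjusted. In the other seven it rejected between 9.1% and 11.0%. The simulation leaves out the baseline covariate and repeated visits, so it illustrates size only.

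**The case against.** The best defence has four parts.

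1. **The SAP does not ignore the factor.** Section 6 names it, 13.1 supplies working code, and 9.3.2 tabulates it at baseline by treatment group, so an imbalance would be seen. This stands. A reader might infer that the stratum was overlooked, or that the whole model choice is open. Neither is supported: 9.1.2 is definite about the listed terms, and what is unsettled is the role of the additional adjusted model.
2. **A role may be stated in text that cannot be read.** Section 7 is largely blacked out, and the text of 9.4.2.3.1 (sensitivity analysis for liver biomarkers) was not available for this review. This stands for ALT, AST and Pro-C3. It carries less weight for MRI-PDFF, whose visible list of supportive analyses has no adjusted MMRM.
3. **The endpoints are not confirmatory.** The primary endpoints are safety and PK. Protocol 8.1 treats the PD p-values as descriptive, and there is no multiplicity adjustment. This lowers the stakes, but it is no reason to prefer the unadjusted model.
4. **The factor is a noisy marker.** Only 36 of 83 subjects are in stratified cohorts, and No mixes unbiopsied subjects, some of whom may have NASH, with others. Its prognostic strength is assumed, and the baseline term may absorb part of it. This limits the likely gain, but adjustment remains nearly free.

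**Conclusion.** The point holds in a limited form. The specified Part 1 MMRM leaves out the factor used to stratify Cohorts 3 and 5, adjustment is optional, and the adjusted code has no role in the visible text. Because placebo is pooled, randomisation does not control the Yes share in the contrasts of interest.

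A reader might go further and say that the design builds in an imbalance, or creates structural confounding. The documents do not support that. The expected imbalance is zero at p = 50%, p is not reported, and the 21% to 79% range needs every unstratified placebo subject to be No or every one to be Yes. The imbalance is uncontrolled, not guaranteed.

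The bias against placebo is probably modest: under 0.15 SD for an assumed 0.5 SD stratum effect at any p, and up to twice that if the effect is 1.0 SD. Between the two sets of doses it can reach 0.25 SD under the 0.5 SD assumption. These figures rest on the planned cohort sizes, a common p in the unstratified cohorts, and assumed stratum effects.

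**What to change.** In SAP 9.1.2, name the MMRM with `biopsy_confirmed_NASH_yn` from Appendix 13.1 as the main model for the PD endpoints analysed by MMRM, MRI-PDFF in particular. Report the unadjusted model as a sensitivity analysis. Reword Section 6 to match, so that the factor is no longer described as only potential. For consistency, add the same term to the analysis step of the multiple-imputation code, which also lacks it.

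This is a free improvement: a sentence or two of text, one degree of freedom, and code that is already written. Protocol 2.3.3 reports that preliminary Part 1 results already exist, so a change made now should be documented in the study report as SAP Section 1 requires, with both models shown.

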8.1. Screened Analysis Set

The Screened Analysis set will consist of all subjects who signed informed consent and undergone screening.

8.2. Randomized Analysis Set

The Randomized Analysis set will consist of all Screened Analysis set subjects who are assigned a randomization number in the study. For analysis purposes, subjects will be analyzed according to the randomized treatment group. Subjects who are replaced will still be counted as randomized subjects.

8.3. Safety Analysis Set

The Safety Analysis set will consist of all randomized subjects who receive at least 1 dose of investigational product. In this population, subjects will be summarized based upon the actual treatment group.

8.4. Pharmacokinetics Analysis Set

The Pharmacokinetics Analysis set will consist of all subjects in the Safety Analysis set who received at least one dose of investigational product and have at least one on study PK measurement. The analysis population for any population PK modeling may be defined separately in a population PK data analysis plan.

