8.3. Populations for Analyses

For purposes of analysis, the following populations are defined:

Population	Description
Screened Analysis set	All enrolled subjects who signed informed consent and undergone screening.
Part 1	
Randomized Analysis set	All enrolled subjects who are assigned a randomization number in the study. For analysis purposes, subjects will be analyzed according to the treatment they were randomized to regardless of actual treatment received.
Safety Analysis set	All randomized subjects who receive at least 1 of study intervention. In this population, subjects will be summarized based upon the study intervention actually received, regardless of the study intervention to which they were randomized.
PK Analysis set	All subjects in the Safety Analysis set who have sufficient data to adequately characterize the trough serum BIO89-100 concentrations and have no other events, or protocol violations that would adversely affect results, such as not completing the full dose. The analysis population for any population pk modeling may be defined separately in a population PK data analysis plan.
PD Analysis set	All subjects in the Safety Analysis set who have measurable post-baseline PD data; subjects will summarized based on the randomized treatment group. Different PD analysis sets may be used for different types of PD endpoints, e.g., MRI-PDFF.
Part 2	
Full Analysis Set	All enrolled subjects who received at least one dose of study intervention. Full Analysis Set will also be used for safety summary in Part 2
PK Analysis Set	All enrolled subjects in the Full Analysis Set who have sufficient data to adequately characterize the trough serum BIO89-100 concentrations and have no other events, or protocol violations that would adversely affect results, such as not completing the full dose.
PD Analysis Set	All enrolled subjects in the Full Analysis Set who have measurable post-baseline PD data. Different PD analysis sets may be used for different types of PD endpoints, e.g., MRI-PDFF.
Biopsy Analysis Set	For Cohort 7 only. All enrolled subjects in the Full Analysis Set and have both baseline and post-baseline biopsies.

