9.2. Pharmacokinetic Analyses

Serum concentration and PK parameter data will be analyzed using the Pharmacokinetics Analysis Set.

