9.5.7. Immunogenicity Analyses

Results of immunogenicity assessment will be summarized by displaying the number of subjects with positive and negative tests. Antibody titers will be listed. Available binding specificity will be listed.

10. Changes to Planned Analysis in the Protocol

There are no changes to the planned analysis in the protocol.

11. Statistical Software

All statistical analyses will be performed using SAS version 9.4 or higher.

12. References

National Heart, Lung and Blood Institute (2020). *Low Blood Pressure*. Retrieved May 19, 2020, from <https://www.nhlbi.nih.gov/health-topics/low-blood-pressure>.

13. Appendix

Table 2 Schedule of Activities for Cohorts 1-4

| Cohorts 1-4 Assessments | Screening Period | | | Treatment Period | | | | | | FU Period | |
|---|------------------|---|----------------|------------------|--|---|---|---|---|-----------|---|
| Study Visit | | | | | | | | | | | |
| Study Day | | | | | | | | | | | |
| Informed consent | X | | | | | | | | | | |
| Medical history/demographics | X | | | | | | | | | | |
| Percutaneous liver biopsy (optional) ^b | X | | | | | | | | | | |
| Prior medications | X | | | | | | | | | | |
| Inclusion and exclusion criteria | X | | X | | | | | | | | |
| Complete physical exam ^c | X | | | | | | | X | | X | X |
| Symptom-directed physical exam ^d | | X | B | P | | B | B | B | B | | |
| Body weight ^e | X | | B | | | B | B | B | B | | |
| Waist and hip measurements | X | | B | | | | | | B | | |
| Fibroscan ^f | X | | | | | | | | | | |
| 12-lead ECG (single) ^g | X | | B | X | | B | B | B | B | X | |
| Urine drug screen and alcohol breath test | X | | X ^h | | | | | | | | |
| Clinical laboratory tests ⁱ | X | X | B | X | | B | B | B | B | X | |
| Cortisol (24 hour urine collection) ^j | X | | | | | | | | | | X |
| Urinalysis | X | | X | | | | | | X | | |
| HbA1c | X | | X | | | | | | | | X |
| Serology ^k | X | | | | | | | | | | |
| TSH | X | | | | | | | | | | |

| Cohorts 1-4 Assessments | Screening Period | | Treatment Period | | | | | | | | | | | | | | FU Period | | | | | | | | | | | | | | | | | |

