7.2. Pharmacokinetics Analysis Set

The PK Analysis Set will consist of all subjects in the Full Analysis Set who have received BIO89-100, and have at least one serum BIO89-100 concentration measurement collected with full dose, and can adequately characterize the trough serum BIO89-100 concentrations.

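### The Part 1 SAP's PK Analysis Set omits the protocol's data-sufficiency and full-dose conditions, so an incomplete dose affecting the Day 1 or Day 29 interval would enter the primary Cmax and AUC summaries at nominal dose

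*SAP*

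**What the plan says.** Protocol 8.3 defines the Part 1 PK Analysis Set as Safety-set subjects who meet two further conditions. They must have "sufficient data to adequately characterize the trough serum BIO89-100 concentrations", and they must "have no other events, or protocol violations that would adversely affect results, such as not completing the full dose".

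Part 1 SAP 8.4 takes Safety-set subjects who were dosed at least once and who "have at least one on study PK measurement". It has no condition on sufficiency of data, on events or violations, or on completeness of the dose.

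This set is the one used for the primary PK endpoints. Part 1 SAP 9.2 states: "Serum concentration and PK parameter data will be analyzed using the Pharmacokinetics Analysis Set". Section 4.1.2 makes Cmax, AUC over the dosing interval, tmax and half-life on Day 1 and Day 29 primary, and 9.2.2 summarizes them by treatment group. Under 5.11, a subject with at least one BIO89-100 dose belongs to the active group of the cohort to which they were randomized.

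Part 1 SAP section 10 says: "There are no changes to the planned analysis in the protocol". Section 1 of the same SAP says that it is based on protocol Version 3.0 of 25 March 2020.

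For comparison, Part 2 SAP 7.2 requires subjects to "have at least one serum BIO89-100 concentration measurement collected with full dose", and also requires that trough concentrations can be adequately characterized.

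**The concern.** The two definitions admit different subjects, and the SAP does not acknowledge the difference. The protocol's example, "such as not completing the full dose", is the kind of event that matters for a summary by dose level: a subject who receives less than the nominal amount has lower exposure for a reason unrelated to the drug's kinetics at that dose.

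The SAP expects such events. Section 9.3.6 counts subjects with at least one partial dose and lists incomplete injections with their volumes and reasons. Section 5.6 counts partial doses as received. No section of the Part 1 SAP removes the affected intervals from the PK summaries or normalizes them for the dose given.

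At stake are the primary Cmax and AUC means, in cohorts of 6 to 14 active subjects. One affected subject can move the mean, and always downward.

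**Working it through.** **1. The definitions side by side**

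| Condition | Protocol 8.3, Part 1 | SAP Part 1, 8.4 |
|---|---|---|
| In the Safety Analysis Set | yes | yes |
| Sufficient data to characterize trough | required | absent; one measurement is enough |
| No distorting events or violations (incomplete dose as example) | required | absent |

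The SAP therefore drops the whole exclusion of distorting events, of which the full-dose condition is only the named example, and also the sufficiency condition.

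**2. The route to the primary summaries**

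The set in 8.4 feeds 9.2. Section 9.2.2 groups by treatment, and 5.11 fixes the group by randomized cohort once any BIO89-100 has been given. Protocol 8.4.2 says that all subjects in the PK population are included in the PK analysis. Nothing along this route filters or rescales an interval after an incomplete dose.

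**3. Size of the effect**

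The plan gives no figure of its own to reproduce. The inputs are:

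- Active subjects per cohort (Part 1 SAP 3.5): 6, 12, 14, 9, 14 and 9 for Cohorts 1 to 6. As a check, 64 active + 19 placebo = 83, which is the stated total.
- Exposure proportional to dose. Protocol 3.2.4 predicts proportional concentrations up to 27 mg QW and 36 mg Q2W.
- One affected subject who receives a fraction *f* of the dose. The documents give neither the number nor the size of partial doses, so *f* is an assumption: 0.5 for illustration, with a range of 0.90 to 0.25.

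The shift in the cohort mean relative to full dosing is:

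- arithmetic mean: −(1 − *f*)/*n*, if the affected subject would otherwise have had average exposure;
- geometric mean: *f*^(1/*n*) − 1, whatever that subject's own exposure.

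For example, with *n* = 9 and *f* = 0.5, the arithmetic shift is −0.5/9 = −5.6% and the geometric shift is 0.5^(1/9) − 1 = −7.4%.

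| Active *n* (cohorts) | Arithmetic, *f* = 0.5 | Geometric, *f* = 0.5 | Arithmetic, *f* = 0.90 to 0.25 | Geometric, *f* = 0.90 to 0.25 |
|---|---|---|---|---|
| 6 (Cohort 1) | −8.3% | −10.9% | −1.7% to −12.5% | −1.7% to −20.6% |
| 9 (Cohorts 4, 6) | −5.6% | −7.4% | −1.1% to −8.3% | −1.2% to −14.3% |
| 12 (Cohort 2) | −4.2% | −5.6% | −0.8% to −6.2% | −0.9% to −10.9% |
| 14 (Cohorts 3, 5) | −3.6% | −4.8% | −0.7% to −5.4% | −0.7% to −9.4% |

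These figures fit Day 1 directly. On Day 29, drug carried over from earlier full doses would make the shift from a single partial dose smaller. If the whole profile scales by *f*, the time of the peak and the rate of decline are unchanged, so tmax and half-life do not shift.

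**The case against.** The strongest objection is about versions. The Part 1 SAP follows protocol Version 3.0. The supplied protocol is a later amendment that already reports preliminary Part 1 results, and the wording of the PK set in Version 3.0 is unknown. A reader might infer that section 10 is false. The documents do not show that; they show a mismatch with the protocol in hand. This objection stands, and it means that Version 3.0 must be checked before section 10 is corrected.

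Second, the handling may be specified elsewhere. Protocol section 8 foresees pharmacokinetic analysis plans, and Part 1 SAP 9.2.2 has a designee calculate the parameters. This is possible, but the Part 1 SAP cites no such rule, and protocol 8.4.2 assigns further PK detail to the SAP.

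Third, the exposure to the problem is narrow. Only incomplete doses that affect the Day 1 or Day 29 interval matter. Those doses are planned for domiciled visits, are given by trained staff, and are confirmed by a second staff member. Incomplete injections and individual concentrations are listed, so an affected interval could be found. All of this lowers the likelihood of a biased mean. It does not supply a rule for when one occurs.

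Fourth, the Part 2 SAP is only a partial comparator. One full-dose sample satisfies its full-dose wording, so it does not repeat the protocol's exclusion. That is correct, and the point does not depend on it.

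Some stronger readings are tempting but unsupported:

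- **Placebo subjects dilute the summaries.** The protocol's set also starts from the Safety set, which includes placebo, and results are presented by treatment group.
- **The exposure margins are compromised.** Protocol 3.2.4 derives them from predicted exposure, using single-dose data and a model, not from Part 1 cohort means.
- **The Part 2 dose choice is affected.** The visible rationale in protocol 4.2.4 rests on MRI-PDFF, ALT and tolerability, with earlier nonclinical, single-dose and modelling work.
- **Partial doses fall mainly on the two-injection regimens.** Nothing in the documents says so.

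**Conclusion.** The point holds as a mismatch of definitions with a modest, conditional effect. SAP 8.4 applied as written would bias a cohort's mean Cmax or AUC downward whenever an incomplete dose affects the Day 1 or Day 29 interval. For one half dose the bias runs from 3.6% to 8.3% on the arithmetic mean and from 4.8% to 10.9% on the geometric mean, depending on cohort size.

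That size rests on dose-proportional PK and an assumed dose fraction. If no incomplete dose touched those intervals, this bias is zero. The effect of dropping the data-sufficiency condition is not quantified here. A reader might extend the conclusion to all four primary PK parameters, but under the same assumption tmax and half-life are unaffected. Whether section 10 is wrong remains open until Version 3.0 has been checked.

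**What to change.** Check the PK set definition in protocol Version 3.0, then do one of the following in the Part 1 SAP:

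1. Restore the conditions of protocol 8.3 in section 8.4: sufficient data to characterize trough, and no events or violations that would adversely affect results, including an incomplete dose.
2. Keep the broad set. Exclude from the Cmax and AUC summaries any Day 1 or Day 29 interval affected by an incomplete dose, and list those intervals separately. Declare this in section 10 as a change, because the protocol's exclusion applies to subjects and this one is narrower, applying to intervals.

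The second option keeps a subject's unaffected interval, which is useful in cohorts this small.

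The cost is a few lines of SAP text and one analysis flag. The volumes of, and reasons for, incomplete injections are already recorded and listed under 9.3.6. The affected summaries would have a slightly smaller *n*.
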